#### **1.0 Background & Rationale**

A constant supply of oxygen is critical for the maintenance of oxygen uptake ( $\dot{V}O_2$ ) during exercise and increasing volumes of oxygen are needed to accommodate increases in exercise intensity. In healthy humans during exercise, the oxygen-carrying molecule hemoglobin is almost fully (>94%) saturated with oxygen, and a difference between the oxygen tension in the alveoli of the lung and the arterial blood exists (20-25 mmHg) but does not necessarily compromise  $\dot{V}O_2$ . However, a subset of otherwise healthy, highly-trained endurance athletes demonstrate a phenomenon termed exercise-induced arterial hypoxemia (EIAH), which refers to a decline in arterial oxyhemoglobin saturation (<92%) during exercise at sea level and is marked by a widened alveolar-arterial oxygen difference (25-40 mmHg) (Dempsey and Wagner, 1999). Over the past half-century, this phenomenon has been well-chronicled in highly-trained and elite athletes across numerous sporting disciplines, especially running ([name] and Stager, 2008; Dempsey et al., 1984; Gavin and Stager, 1999; Harms and Stager, 1995) and cycling (Derchak et al., 2000; Rice et al., 1999; Tanner et al., 2013).

There are four recognized mechanisms for the development of EIAH: inadequate compensatory hyperpnea, diffusion limitation, alveolar ventilation-perfusion ( $\dot{V}_A/\dot{Q}$ ) mismatch, and pulmonary veno-arterial shunt (West and Luks, 2016). EIAH is of concern to athletes because oxyhemoglobin saturation is associated with oxygen transport and, by extension,  $\dot{V}O_{2MAX}$  (Dempsey and Wagner, 1999). Many researchers have investigated the relative contributions of inadequate compensatory hyperpnea,  $\dot{V}_A/\dot{Q}$  mismatch, and veno-arterial shunt to the development of EIAH; however, the contribution of a diffusion limitation has not been as thoroughly examined, despite the fact a diffusion limitation is a viable mechanism by which athletes may ultimately experience EIAH (Prefaut et al., 2000).

There are two theorized routes by which a diffusion limitation could occur during exercise and ultimately lead to EIAH. One mechanism is that EIAH can develop due to an inflammatory response secondary to injury at the interface of the alveoli and pulmonary capillaries (West and Mathieu-Costello, 1995). Numerous studies (Groves et al., 1987; Reeves et al., 1990; Wagner et al., 1986; West and Mathieu-Costello, 1999) have estimated that pulmonary capillary pressure rises high enough to cause injury at the very thin (2-3  $\mu$ m) diffusive barrier, which has been observed in rabbits, dogs, and Thoroughbred racehorses (Birks et al., 1994; Tsukimoto et al., 1991; West et al., 1991). The other mechanism by which a diffusion limitation could occur is through a subclinical pulmonary edema, where fluid from the capillaries leaks into the alveolar space (Hodges et al., 2006). Each of these mechanisms would cause a widening off the diffusive barrier through inflammation following injury or through a thickening of the aqueous barrier between the air in the lung and the blood, respectively, and are not necessarily mutually exclusive and could occur in the same individual.

Histamine is a compound that has been implicated in adding to the diffusion limitation associated with EIAH (Prefaut et al., 1997; Prefaut et al., 2000). Exercise (especially intense exercise) is a well-documented initiator of acute-phase inflammatory processes, including stimulating the action of granulocytic cells (Camus et al., 1993; Suzuki et al., 2002). Indeed, various compounds that appear in greater concentrations in the blood of athletes who experience EIAH have been implicated in signaling and modulating histamine release from its progenitor cells (Horio et al., 2010; Mucci et al., 2000, 2001; Prefaut et al., 2000; Suzuki et al., 2002). Once released from basophils (blood-derived) and mast cells (tissue-derived), histamine is available to bind to the large quantity of H1-receptors available in the pulmonary circuit (Panula et al., 2015). The binding of histamine to pulmonary H1-receptors causes microvascular permeability edema and tissue inflammation characteristic of several pathological conditions (Borriello et al., 2017; Brigham and Owen, 1975; Probst et al., 1978) which, even at subclinical levels not nearly considered anaphylaxis, would ostensibly impair gas exchange during exercise. Furthermore, compounds that inhibit the release of histamine from mast cells (Coyle and Stager, 2001; Prefaut et al., 1997) and competitively inhibit histamine (Coyle and Stager, 2001) have been shown to attenuate EIAH in athletes.

Nearly all of the studies involving EIAH mechanisms and athletes have used either running or cycling as the mode of exercise. However, competitive swimming is an interesting, yet understudied, athletic arena in which to examine EIAH. There is limited evidence (Holmer et al., 1974; Labreche, 2012; Spanoudaki et al., 2004) to suggest that competitive swimmers might experience EIAH. However, it is difficult to draw definitive conclusions from these studies, as they likely either did not have an adequate subject population (Holmer et al., 1974) or did not utilize an exercise protocol with sufficient intensity or duration (Labreche, 2012; Spanoudaki et al., 2004) in which to determine the presence of EIAH. There are numerous plausible mechanisms by which EIAH could develop in swimmers, especially those that are highly-trained. First, swimming occurs 1) in water, with 2) a horizontal body position, and both of these conditions cause an increase in venous return of blood to the heart which would theoretically increase pulmonary capillary pressure (Pendergast et al., 2015). Second, swimmers breathe at incredibly high flow rates (Leahy et al., 2019) with their lungs almost completely inflated (Li, 2016), both of which serve to increase pulmonary capillary pressure (Fu et al., 1992). Third, breathing in competitive swimming is "phase-locked," meaning swimmers can only breathe when their face is out of the water "in-phase" with their swimming stroke, and this ultimately leads to a relative hypoventilation compared to land exercise (Li, 2016). Finally, there is myriad literature linking swimming and pulmonary edema, and this phenomenon is well-chronicled in swimmers of many ages and abilities (Adir et al., 2004; Hohmann et al., 2018).

Therefore, the goals of the present study are twofold:

- 1. To examine whether EIAH occurs in highly-trained swimmers, and
- 2. To examine histamine release as a mechanism by which EIAH occurs in highly-trained athletes.

#### **Objective(s)**

### 2.1 **Primary Objective**

Aim 1. To confirm whether that highly-trained swimmers experience EIAH

It is hypothesized that highly-trained swimmers will experience EIAH, as evidenced by a decrement in peripheral capillary oxyhemoglobin saturation  $(S_pO_2)$  of 5% or greater from rest to submaximal and/or maximal exercise.

Aim 2. To test whether a pharmacological agent that is a competitive inhibitor to histamine (cetirizine HCI) can improve nadir  $S_pO_2$  during submaximal (70 and/or 85%  $\dot{V}O_{2max}$ ) and/or maximal (100%  $\dot{V}O_{2max}$ ) exercise.

It is hypothesized that the pharmacological agents will significantly (p < 0.05) increase nadir SpO2 during all exercise intensities. This will be assessed using a linear mixed model including random effects for subject, subject within-treatment, and subject within-intensity to account for the repeated measures design. Treatments (placebo and cetirizine HCI), intensity (70, 85, and 100% of  $\dot{V}O_{2max}$ ), and the interaction between treatment and intensity will be included. Main effects and interactions will be tested using *F*-tests from a two-way ANOVA.

#### 2.2 Secondary Objective

Aim 3. To test whether degree of desaturation from rest to maximal exercise  $(\Delta S_pO_{2,rest}-S_pO_{2,100\%})$  is correlated with the magnitude of histamine release from rest to maximal exercise  $(\Delta \% H_{rest}-\% H_{100\%})$ .

It is hypothesized that degree of saturation and histamine release will be significantly (p < 0.05) correlated. Correlational strength will be assessed via Pearson correlation coefficient.

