#### 5.0 Study Design

[figure not shown]

Figure 1: Experimental design for proposed study protocol.

The general study protocol is outlined in Figure 1. For the first testing session, participants will report to the Indiana University Human Performance Laboratory to complete a medical screening and, if willing, consent to the procedures of the study. The medical screening will include measurements of height, weight, resting heart rate, resting blood pressure, and resting pulmonary function along with a health history questionnaire. The second testing session consists of an assessment of risk factors for development of EIAH, specifically changes in blood biomarkers pre- and post-swimming exercise. Participants will report to the Counsilman-Billingsley Aquatics Center and complete an exercise protocol designed to elicit an inflammatory response. Venous blood draws will be performed to assess participants' pre-exercise complete blood count and pre- and post-intense exercise concentrations of plasma IL-1 $\beta$ , IL-8, plasma histamine, whole blood histamine, and histamine release. Measurements of hemoglobin concentration and hematocrit will also be performed pre- and post-exercise in order to correct biomarker

concentrations for fluid loss during exercise. Twelve swimmers (n = 6 men, n = 6 women) will be selected for further trials.

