- Graded exercise test: After a self-determined warm-up and a rest period of at least 2 minutes, a progressive maximal exercise test will be performed in a specially constructed, customized variable water flow pool (Endless Pools, Aston, PA, USA), with subjects swimming against a flow rate of approximately 1.5 m·s for men and 1.31 m·s for women tethered to a pulley with a 1.2 and 1 kg mass, respectively. After two minutes, the tethered mass will be increased by 0.2 kg every two minutes until each subject reaches volitional exhaustion. Metabolic and ventilatory variables and SPO2 will be measured as described below. Subjects' heart rates during the tests will be continuously recorded (Cardio Swim HR Monitor; Freelap, Switzerland). VO2MAX will be considered as the maximal value attained during the test, provided at least two of three criteria are met, which will include an RER of greater than 1.05, achievement of 90% of age-predicted maximal heart rate, and an increase in VO2 of less than 0.15 L/min over the previous workload. Plasma histamine, whole blood histamine, and histamine release will be measured before and after this test as previous.
- Constant load tests: Following the maximum exercise test, subjects will perform constant load swimming exercise at approximately 70 and 85% of subjects' previously recorded HRMAX during that session. The tethered mass used to elicit the workloads will be estimated during the first 20-minute rest period by performing a linear regression between HR and tethered mass to approximate the tethered mass that would elicit 70 and 85% of maximum HR. Subjects will swim for 5 minutes. Metabolic and ventilatory variables and SPO2 will be measured as described below. Plasma histamine, whole blood histamine, and histamine release will be measured following these tests as previous.
- Drug administration An opaque sugar-free gelatin capsule (Capsuline, Dania Beach, Florida, USA) will be administered 60 minutes prior to testing and will either be empty (placebo) or contain CH (10 mg; Zyrtec®; Johnson & Johnson, New Brunswick, NJ, USA) according to the visit condition.

Timeline of procedures:

Screening Visit (Visit 1): Once participants arrive at the laboratory, an investigator will
obtain written informed consent after all procedures and study risks are fully explained

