### Table 2: SaO2ear data from Coyle, 2001

A two-way (treatment x intensity) ANOVA using these data produced a Cohen's *f* of 1.22 for the treatment main effect. Therefore, it was determined that using an a priori  $\alpha$  value of 0.05, an estimated twelve subjects are necessary to achieve a power of 0.80. The sample size calculation was conducted using G\*Power 3.1.9.7 (ANOVA: Fixed effects, special, main effects and interactions). Due to the randomized crossover design, all twelve subjects (n = 6 men, n = 6 women) will complete all experimental treatments (PL and CH) at all intensities (70, 85, and 100% of  $\dot{VO}_{2max}$ ).

Previous investigations (Anselme et al., 1994; Mucci et al., 2001) have observed a strong, positive, and significant (r > 0.7; p < 0.05) correlation between  $\Delta$ %H ( $\dot{V}O_{2max}$  - rest) and  $\Delta P_aO_2$  (rest -  $\dot{V}O_{2max}$ ). Using a regression equation ( $\Delta$ %H = 0.0444( $\Delta P_aO_2$ ) - 0.1137; r = 0.80) from Anselme and colleagues (1994), a conservative estimate that a  $\Delta P_aO_2 > 10$  mmHg represents EIAH (Prefaut et al., 2000), we intend to recruit participants for the experimental trials who experience a  $\Delta$ %H > 0.33 during the Selection Exercise Protocol. However, should this inclusion criterion not be met by at least eight subjects, those experiencing the highest  $\Delta$ %H during the Selection Exercise Protocol will be recruited instead.

For proof of principle that EIAH can be prospectively identified using  $\Delta$ %H, a small control group (n=2 men, n=2 women) will also be recruited. For this group, we intend to recruit participants who exhibit the lowest  $\Delta$ %H during the Selection Exercise Protocol. These participants will complete both conditions of the experimental trials.

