In order to test for potential differences in the dependent variables of interest, linear mixed models will be used including random effects for subject, subject within-treatment, and subject within-intensity to account for the repeated measures design. Treatment (PL and CH), intensity (70, 85, and 100% of  $\dot{V}O_{2max}$ ) and the interaction between treatment and intensity will be included. Main effects and interactions will be tested using *F*-tests from a two-way ANOVA. Statistical significance will be assessed using a pre-determined  $\alpha$  level of 0.05. Where significant main effects or interactions are observed, estimated marginal means will be used to test for differences in the drug conditions and adjusted for multiple comparisons using Dunnett's method.

*Hypothesis* 3. The correlation between the change in histamine release ( $\Delta$ %Hpre-%Hpost) and the change in SPO2 at  $\dot{V}O_{2max}$  ( $\Delta$ SPO2rest-SPO2@100%) will be assessed in the pooled experimental and control cohorts (n=12) by a Pearson correlation coefficient using a predetermined  $\alpha$  level of 0.05.

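### Hypothesis 3 rests on one Pearson correlation pooled over 6 men and 6 women with no sex adjustment, so a sex difference in either variable can dilute it and a difference in both can create or mask it

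*Combined protocol and SAP*

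**What the plan says.** Section 2.2 (Aim 3) hypothesises that "degree of saturation and histamine release will be significantly (p < 0.05) correlated", using each swimmer's change from rest to maximal exercise in saturation and in histamine release, and gives the method in one sentence: "Correlational strength will be assessed via Pearson correlation coefficient". The Hypothesis 3 paragraph of section 12.0 says that the correlation "will be assessed in the pooled experimental and control cohorts (n=12) by a Pearson correlation coefficient" at an alpha of 0.05. Neither place mentions sex.

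Sex is nevertheless built into the sample. Section 5.0 states: "Twelve swimmers (n = 6 men, n = 6 women) will be selected for further trials". Section 12.0 says of the low-release swimmers that "a small control group (n=2 men, n=2 women) will also be recruited". The only provision about sex differences is the timing rule in section 7.0, which confines women's visits to the first 7 days following menstruation. That rule deals with hormonal phase at the design stage. It does not adjust the analysis for any other difference between men and women.

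**The concern.** In the crossover comparison of cetirizine with placebo, each swimmer is his or her own control, so a constant difference between the sexes cancels. Hypothesis 3 has no such protection, because it compares swimmers with one another. If men and women differ on average in both variables, the line joining the two sex means contributes to the coefficient whether or not histamine and desaturation are related within either sex. If they differ in one variable only, the difference adds spread unrelated to the association and weakens a real correlation. An equal split gives a fixed sex difference its greatest weight.

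Examining histamine release as a mechanism is one of the two goals stated at the end of section 1.0, and Hypothesis 3 is the planned test of measured release against measured desaturation. With 12 swimmers and no adjustment named in advance, a significant result could be a contrast between men and women, and a null result could hide a real relation. An adjustment added once the data are seen would look chosen for its result.

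**Working it through.** **Inputs from the documents.** n = 12, as 6 men and 6 women (sections 5.0 and 12.0). Alpha 0.05; sidedness is not stated and is taken as two-sided. Expected correlation 0.7, from the statement in section 12.0 that earlier studies found r above 0.7. About 26 swimmers screened, 13 per sex (section 12.0).

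**Inputs that are assumptions.** Normal data. Sex differences dx (histamine change) and dy (desaturation) in within-sex SDs, tried from 0 to 2, because the documents give no value.

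**The plan's own figure.** The 12 is justified for the treatment effect of Aim 2. A fixed-effects F-test with f = 1.22, one numerator df and the 8 cells of Table 2 first reaches 0.80 power at N = 12 (0.878), so the figure reproduces. No power is stated for Hypothesis 3.

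**Step 1, critical values.** r_crit = t / √(t² + df).
- Plain Pearson, 10 df: 2.228 / √(4.964 + 10) = 0.576.
- Adjusted for sex, 9 df: 2.262 / √(5.117 + 9) = 0.602.

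**Step 2, what the pooled coefficient estimates.** For a 50:50 mix with within-sex correlation ρ:

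r_pooled = (ρ + dx·dy/4) / √[(1 + dx²/4)(1 + dy²/4)]

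- ρ = 0, 1 SD in both: 0.25 / 1.25 = 0.20.
- ρ = 0, 2 SD in both: 1 / 2 = 0.50.
- ρ = 0, one variable only: 0.
- ρ = 0.7, 1 SD in one only: 0.7 / √1.25 = 0.63.
- ρ = 0.7, 1 SD in opposite directions: (0.7 − 0.25) / 1.25 = 0.36.

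**Step 3, rejection rates by simulation.** The unselected columns draw 6 + 6 random swimmers (200,000 trials per case). The selected column mimics section 12.0 by keeping the 4 highest and 2 lowest of 13 per sex on histamine change, so 2 × (4 + 2) = 12. It assumes that the controls are within the 12, that selection-day and trial-day changes correlate 0.7 to 1.0, and that shifts are in unselected SDs.

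| Within-sex r | Sex shift | Pooled, unselected | Pooled, selected | Sex-adjusted, unselected |
|---|---|---|---|---|
| 0 | 0.5 SD, both | 5.5% | about 5% | 5% |
| 0 | 1 SD, both | 9.6% | 6.5–8% | 5% |
| 0 | 2 SD, both | 45% | 28–36% | 5% |
| 0 | 1 or 2 SD, one only | 5% | – | 5% |
| 0.7 | none | 78% | 89–95% | 73% |
| 0.7 | 1 SD, one only | 62% | 76–89% | 73% |
| 0.7 | 1 SD, opposite | 14% | 27–43% | 73% |
| 0.7 | 1 SD, same direction | 89% | – | 73% |

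The first four rows are false-positive rates and the rest are power. Dilution needs a shift in one variable only. A spurious correlation needs a shift in both.

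**The case against.** The strongest reply is that nothing in the documents shows a sex difference in either variable, so every figure above is conditional. That stands. At 0.5 SD in both variables the error rate barely moves, and the largest false-positive rates need shifts of 2 SD in both.

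Second, the planned selection of high and low releasers within each sex widens the histamine range and weakens any sex effect. That also stands, and it is why ranges are given. It reduces the problem without removing it.

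Third, the severe masking case requires the sex that releases more histamine to desaturate less, against the mechanism proposed in section 1.0. It is fair not to lean on that case. The milder case, a shift in one variable only, needs no such coincidence.

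Fourth, if the sexes differ in desaturation because they differ in histamine release, adjusting for sex removes real signal. The benchmark correlation in section 12.0 also appears without any mention of adjustment. This is a good reason to keep the plain coefficient and report both.

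Two stronger readings are tempting. A reader might infer that men and women are tested at different efforts, because the graded test has them "tethered to a pulley with a 1.2 and 1 kg mass, respectively", at different flow rates. Those are starting conditions. The increment is the same for both sexes, each swimmer continues to volitional exhaustion, and Aim 3 uses each swimmer's own maximum. A reader might also infer that Hypothesis 3 is the only link the study makes between histamine and desaturation. It is not: Aim 2 tests the mechanism by giving an antihistamine, and the control group is meant to show that histamine release identifies hypoxemia.

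**Conclusion.** The point holds as a gap in a secondary analysis, of uncertain size. The plan pools a fixed 6/6 sex split in one unadjusted between-swimmer correlation. If sex shifts one variable by 1 SD and the within-sex correlation is 0.7, power falls by 16 points with unselected swimmers (78% to 62%) and by roughly 6 to 13 points under the planned selection (95% to 89%, 89% to 76%). If sex shifts both variables and there is no within-sex relation, the false-positive rate is 7–10% at 1 SD and 28–45% at 2 SD, against a nominal 5%.

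These figures rest on normal data, a two-sided test, 12 swimmers and assumed shifts. The documents do not support saying that a sex difference exists, or that the pooled Pearson coefficient is invalid and must be replaced. They support saying that the plan has no means of telling a histamine relation from a difference between men and women.

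**What to change.** In section 2.2 and the Hypothesis 3 paragraph of section 12.0:

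- Keep the pooled Pearson coefficient, and pre-specify beside it the partial correlation of the two changes adjusted for sex. This is equivalent to testing the slope on histamine change in a regression that includes sex. At n = 12 it has 9 df and a critical |r| of 0.602.
- Plot the points with the sexes marked. Separate tests within each sex are not useful, since n = 6 needs |r| above 0.81.
- State that an association between histamine release and desaturation will be claimed only if it holds after adjustment for sex. Say in advance how disagreement between the two coefficients will be read. Accepting whichever is significant would inflate the error rate.
- Confirm whether the four controls are within the 12 or additional to them, and which visit (placebo or cetirizine) supplies the data. The degrees of freedom depend on the first answer: with 16 swimmers the adjusted test would have 16 − 3 = 13.

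The cost is a few sentences of analysis text, since sex is already a selection stratum, and one degree of freedom. If the sexes do not differ, power at r = 0.7 falls from 78% to 73% with unselected swimmers, and by 1–2 points under the planned selection.

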#### 3.0 Outcome Measures/Endpoints

#### **3.1 Primary Outcome Measures**

Plasma histamine, whole blood histamine, histamine release, peripheral capillary oxyhemoglobin saturation, oxygen consumption ( $\dot{V}O_2$ )

